5.1 Inclusion/exclusion criteria

The investigator or his/her designee must ensure that all patients who are offered enrollment in the study meet all of the following inclusion and exclusion criteria:

5.1.1 Inclusion criteria

1. Locally unresectable or metastatic carcinoid or pancreatic neuroendocrine tumors.
2. Tumors must be considered well or moderately differentiated (or low to intermediate grade). Patients with poorly differentiated neuroendocrine carcinomas or small cell carcinomas are excluded from the study.
3. No prior systemic antineoplastic neuroendocrine tumor treatment (including prior somatostatin analogs). However patients who have received a short course of SQ octreotide (<10 days) in the past are eligible if > 1 week has elapsed from their last octreotide injection.
4. Age \geq 18 years.
5. Minimum of four weeks since any major surgery.
6. Measureable disease by RECIST.
7. ECOG performance status \leq 1
8. Life expectancy 12 weeks or more.
9. Adequate bone marrow function as shown by: ANC \geq $1.0 \times 10^9/L$, Platelets \geq $75 \times 10^9/L$, Hgb $>$ 8 g/dL.
10. Adequate liver function as shown by: serum bilirubin \leq 2.0 x upper limit of normal (ULN), and serum transaminases activity \leq 2 x ULN, with the exception of serum transaminases ($<$ 3 x ULN) if the patient has liver metastases.
11. Adequate renal function as shown by serum creatinine \leq 2.0 x ULN.

12. Fasting serum cholesterol ≤ 300 mg/dL OR ≤ 7.75 mmol/L AND fasting triglycerides ≤ 2.5 x ULN. NOTE: In case one or both of these thresholds are exceeded, the patient can only be included after initiation of appropriate lipid lowering medication.
13. Women of childbearing potential must have a negative serum pregnancy test within 14 days of the administration of the first study treatment. Women must not be lactating. Both men and women of childbearing potential must be advised of the importance of using effective birth control measures during the course of the study.
14. Signed informed consent to participate in the study must be obtained from patients after they have been fully informed of the nature and potential risks by the investigator (or his/her designee) with the aid of written information.

5.1.2 Exclusion criteria

1. Uncontrolled brain or leptomeningeal metastases, including patients who continue to require glucocorticoids for brain or leptomeningeal metastases.
2. Patients with prior or concurrent malignancy except for the following: adequately treated basal cell or squamous cell skin cancer, or other adequately treated in situ cancer, or any other cancer from which the patient has been disease free for five years.
3. Patients with uncontrolled diabetes mellitus or a fasting plasma glucose > 1.5 ULN or HbA1c $> 8\%$. Note: At the principle investigator's discretion, non-eligible patients can be re-screened after adequate medical therapy has been instituted.
4. Patients with symptomatic cholelithiasis
5. Patients who have congestive heart failure (NYHA Class III or IV), unstable angina, or a history of acute myocardial infarction within the six months preceding enrollment.
6. Patients who have any severe and/or uncontrolled medical conditions or other conditions that could affect their participation in the study such as:
 - Severely impaired lung function
 - Any active (acute or chronic) or uncontrolled infection/ disorders.
 - Nonmalignant medical illnesses that are uncontrolled or whose control may be jeopardized by the treatment with the study therapy
7. Known hypersensitivity to somatostatin analogues or any component of the pasireotide LAR formulation
8. Corrected QT interval (QTcF) of > 470 msec on screening ECG
9. Risk factors for Torsades de Pointes such as cardiac failure, clinically significant/symptomatic bradycardia.
10. Clinically significant hypokalemia or hypomagnesemia that are not correctable.
11. History of sustained ventricular tachycardia, ventricular fibrillation, advanced heart block, idiopathic syncope thought to be related to ventricular arrhythmia, or congenital long QT syndrome.

12. Concomitant medication(s) known to increase the QT interval (see appendix A)
13. History of noncompliance to medical regimens or unwillingness to comply with the protocol.

6 Study Medication

6.1 Study drug: Pasireotide (SOM 230)

Study drug: pasireotide LAR (long-acting release) i.m. depot injection

Inactive ingredients of pasireotide LAR include: mannitol, carmellose sodium (carboxymethylcellulose sodium), poloxamer 188 and water for injection. For detailed information on pasireotide, please refer to Sections 1.3 and 1.4 or the pasireotide Investigator Brochures.

How supplied

Study drug, Pasireotide LAR i.m. depot injections will be supplied in open-label packaging by Recordati Inc. as a powder in vials containing 20 mg and 40 mg labeled as SOM230 LAR, with ampules containing 2 mL of vehicle (for reconstitution). No syringes or needles will be provided with the pasireotide study drug supplies.

Preparation and storage

Prior to reconstitution, vials should be brought to room temperature. Pasireotide LAR should then be prepared as follows:

Table 6-1 Handling and preparation of pasireotide LAR dose

Dose	Volume to be injected
40 mg	1 x 40 mg vial + 2 mL vehicle: whole volume to be injected
60 mg	1 x 20 mg vial + 1 x 40 mg vial + 2 mL vehicle; whole volume to be injected

Doses should be prepared and administered immediately after preparation.

Recordati Inc. will supply pasireotide LAR as long as the patient remains on study, shows continuous benefit from treatment, and there are no safety concerns. Medication labels will comply with the legal requirements of the U.S. and will be printed in English. The storage conditions for pasireotide LAR will be described on the medication label. Bottles must be stored in a safe, secure location.

All study medication will be supplied to each site directly by Recordati Inc. Under the responsibility of each site's lead investigator, drug supplies must be kept in an appropriate, secure area (e.g. locked cabinet) and stored in accordance with the conditions specified on the drug labels. The investigator must maintain an accurate record of the shipment and dispensing of the study drug in a drug accountability ledger. An accurate record of the date and amount of study drug dispensed to each subject must be available for inspection at any time.

All drug supplies are to be used only for this protocol and not for any other purpose. Unless specifically instructed by Recordati Inc., the investigator must not destroy any drug labels, or any unused drug supply.

The storage condition for the study drug will be described on the medication label.

Administration

Pasireotide LAR will be administered i.m., intragluteally, every 4 weeks. The starting dose will be 60 mg. The reconstitution has to be performed just prior to administration of the suspension. A minimal standing time can be tolerated for the reconstituted suspension in the vial. Prior to administration, the reconstituted suspension in the vial should be shaken again before withdrawal in the syringe. The i.m. injection must be given immediately after withdrawal of the reconstituted suspension from the vial to the syringe. All dosages prescribed and dispensed to the patient and all dose changes during the study must be recorded. Recordati Inc. will supply pasireotide free of charge for study participants.

6.2 Permitted study drug adjustments

Toxicity will be assessed using the NCI-CTC for Adverse Events, version 4.0 (CTCAEv4.0, (<http://evs.nci.nih.gov/ftp1/CTCAE/About.html>)). For patients who are unable to tolerate pasireotide 60mg every 4 weeks, the dose may be changed to 40mg every 4 weeks (see table 6-2).

Table 6-2 Criteria for dose-modification of pasireotide

Adverse event	Action
*Grade \leq 2	No study drug adjustments
*Grade \geq 3 and judged as at least possibly drug related	
 • Reduce dose to 40mg • If AE improves to grade \leq2 before the next administration, increase dose to 60mg. If the dose is increased and that AE recurs at CTC grade \geq 3 the dose will be reduced back to the lower dose and shall not be increased again during the study period. • If AE does not improve to grade \leq2 on the lower dose before the next administration, the patient will discontinue the study drug and be followed for safety.

*This guidance should be use for all probably related AEs except for changes in blood glucose which should be addressed as described in Section 6.3.1 and changes in QTc interval which should be addressed as described in Section 6.3.2..
	

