3.3 Exploratory endpoint

- To assess the correlation between somatostatin receptor profiling (via immunohistochemistry) and PFS

4 Study design

This is a multi-institutional, prospective phase II open-label trial.

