6.3.5 Study drug discontinuation

Patients experiencing unacceptable toxicity (AE grade 3 or higher) that the investigator considers directly attributable to the study drug should have their dose adjusted as per dose modification guidelines in Table 6-2. If a patient has already decreased 1 dose level, no further dose reduction is permitted, and the patient will be permanently discontinued from treatment. For QTc related protocol discontinuation, please see section 6.3.2. For LFT related protocol discontinuation, see section 6.3.3.

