6.4 End of treatment

Patients may voluntarily withdraw from the study or be dropped from it at the discretion of the investigator at any time. Patients will be withdrawn from the study if any of the following occur:

- Disease progression
- Death
- Withdrawal of consent
- Delay of treatment >21 days.
- Uncontrolled diabetes mellitus (DM)
- Pregnancy
- Adverse event(s) \geq grade 3 despite dose reduction
- QTc prolongation (see section 6.3.2)

7 Visit schedule and assessments

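### Table 6-2 and section 6.3.5, read literally, conflict on whether a patient whose grade 3 or higher event recurs after return to 60 mg continues at 40 mg or stops for good

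*Combined protocol and SAP*

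**What the plan says.** The protocol has a starting dose of 60 mg every 4 weeks and one lower level, 40 mg (sections 2.1 and 6.2). Three places govern a grade 3 or higher event attributed to the drug.

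- **Section 6.2, Table 6-2.** The dose goes down to 40 mg. If the event improves to grade 2 or lower, the instruction is "before the next administration, increase dose to 60mg". If the same event then returns at grade 3 or higher, "the dose will be reduced back to the lower dose and shall not be increased again during the study period". If the event does not improve at the reduced dose, study drug is stopped.
- **Section 6.3.5.** Such patients "should have their dose adjusted as per dose modification guidelines in Table 6-2". Two sentences follow on directly from each other, and the second reads: "If a patient has already decreased 1 dose level, no further dose reduction is permitted, and the patient will be permanently discontinued from treatment".
- **Section 6.4.** Withdrawal criteria include an adverse event of at least "grade 3 despite dose reduction".

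Table 8.4 censors PFS at the last radiologic assessment when treatment is discontinued for toxicity. On setting, section 4 says: "This is a multi-institutional, prospective phase II open-label trial".

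**The concern.** Table 6-2 provides expressly for a second reduction after re-escalation. Section 6.3.5 looks back to whether a reduction has already occurred, makes no exception for a patient who has gone back to 60 mg, and rules a second reduction out. An investigator facing that patient cannot satisfy both texts as written.

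Two things are at stake. The first is conduct and safety: the texts decide whether a patient with a recurrent severe related event receives more drug. The second is the primary endpoint. A patient who is stopped is censored under Table 8.4, while a patient who continues is still scanned on schedule and can still contribute a progression or a 12-month progression-free status.

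**Working it through.** The documents give no figure on this point, so there is none to reproduce. The check applies each text to every dose path the protocol allows, with a related grade 3 or higher event on the last dose listed. Section 6.3.5 is read in two ways: literally (the patient has ever been reduced) and as a floor (the patient is now at 40 mg). In rows ending at 40 mg, the event is assumed not to improve to grade 2 or lower.

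| Doses so far (mg) | Table 6-2 | 6.3.5, literal | 6.3.5, as a floor |
|---|---|---|---|
| 60 | reduce to 40 | reduce to 40 (via Table 6-2) | reduce to 40 (via Table 6-2) |
| 60, 40 | discontinue | discontinue | discontinue |
| 60, 40, 60 | reduce to 40, continue, no later increase | **discontinue** | reduce to 40 (via Table 6-2) |
| 60, 40, 60, 40 | discontinue | discontinue | discontinue |

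The texts part company on one row only: recurrence after return to 60 mg. On that row the answer turns entirely on how section 6.3.5 is read. Section 6.4 does not break the tie. Its phrase on dose reduction can mean an event while at 40 mg or an event at any time after a reduction.

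**A different event after re-escalation.** Table 6-2's recurrence wording covers only the event that caused the reduction. For a new grade 3 or higher event at 60 mg, one has to infer that the first bullet starts again and gives 40 mg. Literal section 6.3.5 gives discontinuation. This is a gap in Table 6-2 rather than a second express contradiction.

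**Timing inside Table 6-2.** Injections are 4 weeks apart. The first bullet reduces the dose, and the second restores 60 mg on improvement ahead of the next injection.

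- If the interval meant is the one after the 60 mg injection that preceded the event, a patient who improves in time returns to 60 mg without receiving any 40 mg injection.
- If it is the interval after a 40 mg injection, one reduced dose has been given.

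The third bullet speaks of the patient being at the lower dose, which presupposes the second sequence. The table does not say which applies to the second bullet.

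**Route to PFS.** Discontinuation for toxicity leads to an end-of-treatment scan (section 7.3) and censoring at the last scan (Table 8.4), so a later progression is not counted. Continuation leads to further scans every 3 cycles (section 7.2), reduced in frequency after 2 years, so a later progression is counted. The number of patients affected would be the sample size times the probability of this path. The documents give no value for that probability, so no effect size follows.

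**The case against.** The strongest reply is that section 6.3.5 is not a rival rule. It sends the reader to Table 6-2 first, only one level exists below 60 mg, and its next sentence may simply state that a patient at 40 mg can go no lower. Section 6.4 is compatible with that reading, and Table 6-2 is the text that addresses recurrence expressly. This reading is reasonable and removes the conflict on the named path. It stands as a possible interpretation but not as the protocol's stated meaning. The sentence refers to a past reduction, not to the current dose, and no order of precedence is given.

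The path is also narrow. It needs a related grade 3 or higher event, improvement, re-escalation and recurrence. Table 6-2's footnote takes out glucose and QTc changes, and section 6.3.3 has its own rules for liver tests. That stands, and it limits the likely number of patients.

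The bullets of Table 6-2 can likewise be read as a sequence in which a 40 mg injection always comes first. That is fair, and it is why the timing point is called an ambiguity and kept secondary.

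The censoring rule in Table 8.4 applies to every toxicity stop and is a separate matter. The end-of-treatment scan also limits unobserved time before censoring. Both are correct. The link made here is only that the unclear dosing rule decides who falls under that censoring rule.

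Two stronger readings are tempting. A reader might infer that sites do treat the same patient differently. The documents show no such divergence, only the conditions for it. A reader might also take one patient's share of the sample (1/38 = 2.6% to 1/30 = 3.3%, using the sizes in sections 11.1 and 11.2) as the effect on the 12-month PFS rate. It is not an effect size. A change in that rate would also require the path to occur, a stop before 12 months, and an outcome classified differently as a result.

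**Conclusion.** The point holds as a conflict between the literal texts of Table 6-2 and section 6.3.5, confined to a grade 3 or higher event recurring after return to 60 mg. Section 6.4 leaves it open. It depends on reading section 6.3.5 by its words; if that section means a patient currently at 40 mg, the conflict on this path is gone, and the remaining defect is that the protocol does not say so.

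Inconsistent stop or continue decisions are foreseeable in a multi-institutional trial. An effect on PFS through Table 8.4 is possible, but it is not shown and cannot be sized from the documents. The different-event gap and the injection-interval ambiguity are real but secondary. The matter deserves correction because it governs continued exposure after severe related toxicity and is cheap to resolve, not because a bias in the primary result has been demonstrated.

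**What to change.** 1. Reconcile Table 6-2, section 6.3.5 and section 6.4 so that one rule covers a grade 3 or higher event after re-escalation, whether it is the same event or a different one. Say in section 6.3.5 whether its limit refers to the current dose or to any past reduction, and make section 6.4 match.
2. State in Table 6-2 which injection interval the second and third bullets refer to, so that both describe the same sequence.
3. If patients have already been treated under the present wording, list those who reached this path and how each was classified under Table 8.4. Section 6.1 already requires dose changes to be recorded, so the dosing data should exist.

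Which rule stands is for the sponsor and investigators to decide.

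The cost is a change of protocol wording and a memo to sites, with no added procedures. Section 14 requires a written amendment for any non-administrative change, with IRB approval at each center where it significantly affects subject safety.

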6.3 Follow-up for toxicities

Patients who interrupt or permanently discontinue pasireotide due to an adverse event or abnormal laboratory value must be followed at least weekly for 28 days after the last dose of pasireotide, and subsequently at monthly intervals until resolution or stabilization of the event,

whichever comes first. If a patient requires a dose delay of > 21 days from the intended day of the next scheduled dose, then the patient should be discontinued from the study.

All patients will be followed for adverse events and serious adverse events for 28 days following the last dose of pasireotide.

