6.3.3 Management Guidelines for Abnormal Liver Function

Table 6-3-3: SOM230 Abnormal liver function management

Perform within **72 hours** of awareness of abnormal LFTs:

- Perform liver-directed medical history and physical examination (i.e. assess occupational hazards, concomitant medications including OTC meds, intercurrent illness, etc)
- Liver chemistry tests: ALT, AST, total bilirubin, (fractionate to direct/indirect bilirubin if total bilirubin is $> 2.0x$ ULN), Alb, PT (INR), ALP, and GGT
- Perform hepatitis screen: anti-HAV, IgM (to confirm acute hepatitis A), HbsAg, Anti-HBc, anti-HCV (if positive PCR viral load should be assessed), Anti-HEV, ANA antibodies, anti-smooth muscle anti-bodies, CMV, EBV
- Perform abdominal ultrasound (liver and biliary tree)
- Collect PK sample and record the dose level and the dosing time for the last dose the patient has taken prior to PK sampling.

Liver chemistry tests should be monitored **every 3-4 days** for s.c. and LAR studies until resolution or return to baseline status.

For ALT or AST > 5x ULN and ≤ 8x ULN:

Study medication should be temporarily interrupted and liver chemistry tests monitored **every 3-4 days** for s.c. and LAR studies until resolution or return to baseline

If resolution or return to baseline does not occur after 2 weeks, the patient should be discontinued.

If ALT or AST returns to less than 5x ULN, study drug can be resumed and patient can continue study per protocol

If ALT or AST rises above 5x ULN anytime after study drug is resumed, then study drug should be discontinued immediately.

Table 6-3-3-1: SOM230 Abnormal liver function discontinuation criteria Hepatic-related discontinuation criteria for all ongoing studies

Study medication should be discontinued immediately if any of the discontinuation criteria below are met:

ALT or AST > 3x ULN and Total Bilirubin > 2x ULN and ALP < 2x ULN

ALT or AST > 5x ULN and ≤ 8x ULN persistent for more than 2 weeks

ALT or AST > 8x ULN

Re-challenge of study medication is prohibited once discontinuation criteria are met.

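### The Table 6-2 footnote does not except ALT/AST rises, so read literally it gives 40 mg where section 6.3.3 directs a hold: a minor safety-rule inconsistency

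*Combined protocol and SAP*

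**What the plan says.** In section 6.2, Table 6-2 answers an adverse event of grade 3 or higher, at least possibly drug related, with a reduction to 40 mg. If the event settles to grade 2 or lower before the next dose, the dose returns to 60 mg. If it then recurs at grade 3 or higher, the patient goes back to 40 mg and stays there. If it does not settle "on the lower dose before the next administration, the patient will discontinue the study drug and be followed for safety". The footnote sets the scope: "This guidance should be use for all probably related AEs". Two kinds of event are then carved out and sent to their own sections, 6.3.1 and 6.3.2, in these words: "except for changes in blood glucose which should be addressed as described in Section 6.3.1 and changes in QTc interval which should be addressed". It lists no other exception.

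Section 6.3.3 has its own rule for ALT or AST above 5 and up to 8 times ULN: "Study medication should be temporarily interrupted and liver chemistry tests monitored" every 3 to 4 days. It continues: "If ALT or AST returns to less than 5x ULN, study drug can be resumed and patient can continue study per protocol". Any rise above 5 times ULN after restarting means stopping immediately. Table 6-3-3-1 lists further stopping criteria, including "ALT or AST > 5x ULN and ≤ 8x ULN persistent for more than 2 weeks" and any value above 8 times ULN.

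Section 6.3.5 sends attributable toxicity of grade 3 or higher to Table 6-2, and separately refers the reader to 6.3.3 for liver-related discontinuation. Section 6.3 provides for interruption in general terms: "Patients who interrupt or permanently discontinue pasireotide due to an adverse event or abnormal laboratory value must be followed". It also sets a limit on delay: "If a patient requires a dose delay of > 21 days from the intended day of the next scheduled dose", the patient leaves the study. Appendix E is titled as a liver-function management algorithm, but its content is not in the text available for this review.

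**The concern.** The footnote reads as a complete list of exceptions. Glucose (6.3.1) and QTc (6.3.2) are on it. Liver function (6.3.3), the third organ-specific rule in the same series, is not. A site could fairly conclude that a drug-related ALT/AST rise recorded as a grade 3 or higher event follows the table. The table speaks of improvement on the lower dose, which suggests that 40 mg is given while the event persists.

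At stake is uniform handling of a safety rule in a multi-institutional trial. One site might inject a 4-week depot at 40 mg while another withholds it for the same value, and a depot dose given in error is a full cycle's exposure. The protocol's background sections report transient liver-test abnormalities with this drug (1.4.1 and 1.4.2.1), so the situation is plausible. The documents give no frequency for it in this population.

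**Working it through.** The plan states no figure to reproduce. The check compares the two rules and then asks whether the schedule lets them collide.

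**Side by side**, for a drug-related ALT/AST rise of >5 to 8 times ULN recorded as a grade 3 or higher event:

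| Step | Table 6-2, read literally | Section 6.3.3 |
|---|---|---|
| Rise found | Reduce to 40 mg; no hold | Hold; retest every 3–4 days |
| Condition for further dosing | Grade 2 or lower on the lower dose by the next administration | ALT/AST below 5 times ULN |
| Dose on resumption | 40 mg, or 60 mg after improvement | Not stated |
| Recurrence after restart | Back to 40 mg, treatment continues | Immediate discontinuation |

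The first row can be reconciled: hold under 6.3.3, then resume at 40 mg. The last row cannot, because one rule continues treatment and the other ends it. On recurrence, however, the discontinuation pointer in 6.3.5 does lead to 6.3.3. No cross-reference in the available text reaches the temporary hold. Values above 8 times ULN are covered by the 6.3.5 pointer.

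**Timing.** Inputs: a cycle of 28 ± 3 days (4.1); liver tests 21 days after injections 1 and 3 (7.2); retests every 3–4 days and a two-week criterion (6.3.3); a 21-day limit on delay (6.3); AST and ALT in the cycle-start panel (Table 7-3, footnote e). Take the injection as day 0.

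- Next injection due: 28 − 3 = day 25 to 28 + 3 = day 31.
- Day-21 test to next injection: 25 − 21 = 4 days to 31 − 21 = 10 days.
- Retests in that gap: floor(4/4) = 1 to floor(10/3) = 3.
- Two-week point: 21 + 14 = day 35. The persistence criterion therefore cannot be met before the injection falls due. In this band, only the hold prevents that injection.
- Cycle-start panel: drawn on the injection day, so the gap is 0 days.

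**Does the hold that 6.3.3 already directs fit the 21-day limit?** To the two-week point:

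- Day-21 finding: 35 − 31 = 4 to 35 − 25 = 10 days' delay, or 35 − 28 = 7 days from nominal day 28.
- Cycle-start finding: 14 days' delay, or (25 + 14) − 28 = 11 to (31 + 14) − 28 = 17 days from nominal day 28.

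All are below 21 days.

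**The case against.** The strongest reply is that the rules answer different questions. Table 6-2 sets a dose level and 6.3.3 sets timing. The text introducing the table is permissive about the change to 40 mg, and nothing in it cancels 6.3.3, which is specific and unconditional. Section 6.3.5 already leads sites to 6.3.3, where the hold sits beside the stopping criteria and the 72-hour work-up. Section 6.3 anticipates interruption for an abnormal laboratory value. Appendix E may set out the sequence explicitly.

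Most of this stands. A reader might infer that the protocol orders an injection while ALT/AST is above 5 times ULN. It does not: a site doing so would be disregarding an express instruction in 6.3.3. A reader might also infer that the plan never says which section governs. That cannot be claimed while the content of Appendix E is unseen.

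The overlap is also conditional. The protocol grades by CTCAE v4.0 but prints no ALT/AST cut-offs, and 9.1 counts a laboratory value as an adverse event only if it causes symptoms, is clinically significant or needs therapy. The cycle-start case further assumes that results are back before the same-visit injection, which the documents do not say.

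Three things survive: an exception list that omits the liver rule, a pointer in 6.3.5 that covers discontinuation but not the hold, and recurrence instructions that differ outright.

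**Conclusion.** The inconsistency is real and minor. It is confined to a drug-related ALT/AST rise recorded as a grade 3 or higher event. For the hold, the value must also lie above 5 and up to 8 times ULN and still be above 5 when an injection is due. For recurrence, it must rise above 5 times ULN after restarting. The schedule permits the hold case with 4 to 10 days' notice after the day-21 tests and none at the cycle-start panel. Its frequency is unknown.

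The conclusion rests on the literal reach of the footnote and on the grade being met. It makes no claim about the grade 2 or lower row. A careful site would probably follow 6.3.3. A reader might go further and infer bias in PFS, but nothing in the documents links this wording to the primary endpoint, and sample size, power and alpha are untouched.

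**What to change.** Add to the Table 6-2 footnote: *For ALT/AST elevations, the interruption, resumption and discontinuation rules in Section 6.3.3 take precedence: do not inject while ALT or AST is >5x ULN. Table 6-2 otherwise continues to apply, including the reduction to 40 mg on resumption and other grade ≥3 hepatic events.* In 6.3.5, change the pointer to: *LFT related interruption or discontinuation, see section 6.3.3.* Check that Appendix E agrees.

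A blanket exemption of abnormal liver function from Table 6-2 would be simpler but worse. Section 6.3.3 names no dose on resumption, so the 40 mg step would be lost. Its hold and stop rules are triggered by ALT/AST, with bilirubin counting only alongside an ALT/AST rise, so an isolated grade 3 or higher bilirubin or ALP event would be left with no dose-modification rule.

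The cost is two sentences in the footnote and a few words in 6.3.5, handled under the amendment procedure in section 14. No visit or test changes. The delays worked out above are not a cost of the edit, because 6.3.3 already directs the hold.
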